CRITERIA FOR EVALUATION: Efficacy: Primary efficacy endpoint: 
Change of the hFVIII activity, as measured by chromogenic substrate assay, during Weeks 49-52 post-BMN 270 infusion from baseline. Each subject's hFVIII activity during Weeks 49-52 is defined as the median of the values obtained during this 4-week window. Values for hFVIII activity will be excluded if obtained within 72 hours since the last infusion of exogenous FVIII protein concentrates. Secondary efficacy endpoints: 
Change from baseline in the annualized utilization (IU/kg/year) and infusion rate (number/year) of exogenous FVIII replacement therapy from Week 5 post-BMN 270 infusion to last visit by data cutoff (for Week 52 analysis) for subjects receiving FVIII prophylaxis during the 12 months prior to study entry, or change from baseline in the annualized utilization (mg/kg/year) of emicizumab from Week 27 post-BMN 270 infusion to last visit by data cutoff (for Week 52 analysis) for subjects receiving prior emicizumab prophylaxis.Change from baseline in the annualized number of bleeding episodes requiring exogenous FVIII replacement treatment (annualized bleeding rate, ABR) from Week 5 post-BMN 270 infusion to last visit by data cutoff (for Week 52 analysis) for subjects receiving prior FVIII prophylaxis, or from Week 27 post-BMN 270 infusion to last visit by data cutoff (for Week 52 analysis) for subjects receiving prior emicizumab prophylaxisChange from baseline in the total score of Haemo-QoL-A at Week 52 post-BMN 270 infusion		

NAME OF COMPANY BioMarin Pharmaceutical Inc. [name] [name]	SUMMARY TABLE Referring to Part of the Dossier: Volume: Page: Reference:	FOR NATIONAL AUTHORITY USE ONLY:

NAME OF FINISHED PRODUCT: BMN 270
 
NAME OF ACTIVE INGREDIENT: AAV5-hFVIII-SQ
 
Tertiary efficacy endpoints:
 
• Change from baseline in the EQ-5D-5L score at Week 52 post-BMN 270 infusion.• Change from baseline in the Work Productivity and Activity Impairment plus Classroom Impairment Questions: Hemophilia Specific (WPAI+CIQ:HS) score at Week 52 post-BMN 270 infusion.• Change from baseline in Patient Reported Outcomes, Burdens, and Experiences (PROBE) score at Week 52 post-BMN 270 infusion.		

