7.3.1 Optional Liver Biopsy Rationale

The usual pattern of response in hFVIII activity observed so far after administration of BMN 270 demonstrates peak expression levels during the first 6-12 months post-treatment followed by a decline to a steady-state level of expression thereafter. One of the explanations may lie in the kinetics of vector genome processing, which involves a series of steps such as DNA degradation and repair, annealing, and circularization that can result in the formation of

stable, double-stranded, circularized transgene DNA forms. It is these circularized DNA species that are thought to be associated with long-term, persistent expression of the gene product in target cells. Examination of transduced hepatocytes from subjects treated with BMN 270 in the 270-303 study will help to establish whether DNA circularization may occur and could account for the long-term hFVIII expression observed in humans.

Additionally, health of the liver after gene transduction has been monitored indirectly by periodic assessments of hepatic enzymes released into the blood stream. Transient, post-treatment elevations in ALT levels have been observed in the majority of subjects, as well as inter-subject variability in post-therapy FVIII activity levels. Neither the reasons for nor the significance of the ALT elevations or the variations in response to FVIII gene therapy are known. Moreover, the effects of BMN 270 on hepatic tissue structure and function are also currently unknown. Finally, a call to incorporate liver biopsy sub-studies into gene therapy trials for hemophilia has been issued by medical and scientific leaders in the field to help illuminate these and other questions ([National Hemophilia Foundation 2019](#)).

The purpose of this exploratory sub-study is to provide a better understanding of the long-term gene expression related to genome circularization, health of the liver, and variation in FVIII activity levels observed after gene therapy with BMN 270. With use of prophylactic corticosteroids, it is believed that there will be stable hepatic function and FVIII activity expression, with tolerance of prophylactic corticosteroid therapy and no change to the risk of thromboembolism. This sub-study aims to evaluate the effect on the liver by performing liver biopsies at approximately Week 26, Week 52, and/or during Years 2-5.

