In subjects who experience recurring bleeding episodes, the Investigator and Medical Monitor will discuss whether to resume prior FVIII prophylaxis. Subjects who do not respond to BMN 270 treatment (ie, treatment failure manifesting as failure to achieve FVIII activity \geq 5 IU/dL by Week 52 and inability to maintain independence from prophylactic FVIII replacement therapy due to joint bleeding episodes, in the judgment of the Investigator) may, at the Investigator's discretion and after discussion with the Medical Monitor or Sponsor-designated Data Monitor, follow an abbreviated visit schedule after Week 52 of the study by attending only the Q12W and End of Year visits during Years 2-5. Subjects who are not attending the Q4W/Q6W visits during Years 2-5 may receive a scheduled monthly follow-up telephone call from the site to ask about adverse events, concomitant medications, and bleeding events/FVIII replacement usage.

There will be an ongoing review of individual subject safety by the Medical Monitor, and both safety and efficacy data by the DMC. Patients will receive prophylactic corticosteroids with tapering of the dosage based upon consideration of ALT values, FVIII activity levels, and as indicated, consultation with the Investigator and the Medical Monitor. Reactive oral corticosteroids may be initiated if a subject's ALT values increase from baseline levels, after consultation between the Investigator and the Medical Monitor (refer to Section 9.4.8.2).

In case of a safety concern, additional unscheduled laboratory tests may be performed locally (at the Investigator's discretion) in order to facilitate timely and appropriate clinical management decisions; where possible, a matched sample for testing at the central laboratory should be collected (using the Unscheduled Visit lab kit) at the same time as the local unscheduled sample.

Any safety signal may trigger a review of the data and possible additional immunogenicity studies or other diagnostics deemed necessary that include an assessment of cellular immune responses using collected peripheral blood mononuclear cells (PBMCs).

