^c Includes FVIII activity level (chromogenic substrate FVIII assay and one-stage clotting FVIII assay), chromogenic Nijmegen-Bethesda Assay for hFVIII inhibitor level, and coagulation exploratory assay. Chromogenic Nijmegen-Bethesda Assay for hFVIII inhibitor level will be tested as deemed necessary by the Sponsor. If a subject has used FVIII within 72 hours of a measurement day, all efforts should be made to obtain FVIII activity measurements when a 72-hour interval without FVIII use is achieved; the 72-hour wash-out period is only intended for subjects who have achieved FVIII ≥ 5 IU/dL at 16 weeks after BMN 270 infusion and who have not resumed FVIII replacement therapy. If FVIII levels are elevated or stable over the course of several weeks, assessment of FVIII activity may be adjusted based on discussion between the Medical Monitor and the Investigator. A D-dimer may be considered under circumstances in which FVIII activity levels are above the normal physiological range and/or if there is a concern for a venous thromboembolism.

^d Collection for each matrix to occur until at least 3 consecutive results below the limit of detection are obtained; longer collection and testing may be performed based on batch testing schedules, result turnaround times, or discussions between Medical Monitor and Investigator.

^e Blood samples will be collected to evaluate biochemical, molecular, cellular, and genetic/genomic aspects relevant to hemophilia A, coagulation, and/or AAV gene transfer, and to develop assays used for these evaluations. Subjects may choose to opt out of the exploratory genetic/genomic research being done to study or try to discover genes that are not yet known to be associated with hemophilia A. While exploratory samples will be collected at the time points indicated above, testing of these samples (including those for any other exploratory assessments) will be performed only as deemed necessary by the Sponsor.

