9.7.2 Primary Efficacy Variables

9.7.2.1 FVIII Activity

The primary efficacy variable is change of the hFVIII activity, as measured by chromogenic substrate assay during Weeks 49-52 post-BMN 270 infusion from baseline.

If a subject has used FVIII within 72 hours of a measurement day, all efforts should be made to obtain FVIII activity measurements when a 72-hour interval without FVIII use is achieved; The 72-hour wash-out period is only intended for subjects who have achieved $FVIII \geq 5 \text{ IU/dL}$ at the end of 16 weeks after BMN 270 infusion and who have not resumed FVIII replacement therapy.

Note that fluctuations in FVIII activity after gene therapy are common, and more frequent monitoring of FVIII activity levels is not needed in the absence of a concurrent or recent ALT elevation or upon consultation between the Investigator and the Medical Monitor.

Details on collecting FVIII activity samples are included in the Laboratory Manual.

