14.2 Primary Efficacy Endpoint

For the primary efficacy endpoint at Week 52 (ie, the change in the hFVIII activity during Weeks 49-52 post-BMN 270 infusion from baseline, as measured by chromogenic substrate assay), a one-sample t-test will be used to test the null hypothesis that the change is 0 or less against the alternative hypothesis that the change is greater than 0 at the 1-sided significance level of 0.025 (or equivalently, at the 2-sided significance level of 0.05). Baseline value of 1 IU/dL (eligible subjects must have residual FVIII levels \leq 1 IU/dL as evidenced by medical history) will be used in the calculation of change from baseline since all the subjects will be on prophylactic hemophilia therapy prior to BMN 270 infusion where the FVIII activity level cannot be reliably measured. Descriptive summaries of the proportions of subjects whose hFVIII activity during Weeks 49-52 is greater than or equal to select thresholds, such as 5, 15, 25, 30, and 40 IU/dL, and the confidence intervals of the proportions will also be provided.

For a subject with a missing value of the primary endpoint, the median value in the subject's last 4-week window containing a valid observation will be used. Additional analyses will be

conducted to examine the sensitivity of the results to the handling of missing data, including analysis using observed cases, and a mixed model for repeated measures (MMRM) approach. Further detail will be provided in the SAP.

The analyses for the primary endpoint will be performed using the analysis populations as defined in Section 14.9.

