14.3 Secondary Efficacy Endpoints

The analyses of the secondary efficacy endpoints will be descriptive. Mean and associated 95% confidence interval will be provided for the following secondary endpoints, where the baseline value will be derived from the data in the approximately 12-month period prior to BMN 270 infusion:

- For subjects receiving FVIII prophylaxis prior to study entry, change from baseline in the annualized utilization (IU/kg/year) of exogenous FVIII replacement therapy from Week 5 post BMN 270 infusion to last visit by data cutoff (for Week 52 analysis); and separately, for subjects receiving prior emicizumab prophylaxis, change from baseline in the annualized utilization (mg/kg/year) of emicizumab from Week 27 post BMN 270 infusion to last visit by data cutoff (for Week 52 analysis)
- For subjects receiving FVIII prophylaxis prior to study entry, change from baseline in the annualized infusion rate (number/year) of exogenous FVIII replacement therapy from Week 5 post BMN 270 infusion to last visit by data cutoff (for Week 52 analysis); and separately for subjects receiving prior emicizumab prophylaxis, change from baseline in the annualized utilization (mg/kg/year) of emicizumab from Week 27 post BMN 270 to last visit by data cutoff (for Week 52 analysis) infusion
- Change from baseline in the annualized number of bleeding episodes (number/year) requiring exogenous FVIII replacement treatment from Week 5 post-BMN 270 infusion to last visit by data cutoff (for Week 52 analysis) for subjects receiving prior FVIII prophylaxis, or from Week 27 post-BMN 270 infusion to last visit by data cutoff (for Week 52 analysis) for subjects receiving prior emicizumab prophylaxis from baseline

Mean change from baseline and associated 95% confidence interval will be calculated for the total score of Haemo-QoL-A at Week 52 post-BMN 270 infusion as well.

The missing value of the change for annualized utilization and annualized infusion rate will be imputed as 0. The missing value of the change for annualized number of bleeding episodes will be imputed using the median value of the changes of all observed cases.

A sensitivity analysis is planned to analyze ABR using a generalized linear mixed model assuming negative binomial as the underlying distribution. The model will include period (pre- to post-BMN 270 infusion) as the only factor, repeated within subject. The actual

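### In the primary analysis, a subject who responds, loses response and resumes FVIII prophylaxis is usually given an earlier FVIII value, which can overstate the mean and the threshold proportions

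*Protocol*

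**What the plan says.** The primary endpoint is the change in chromogenic FVIII activity from a fixed baseline of 1 IU/dL to the subject's median over Weeks 49-52. Several provisions decide what happens to a subject who has gone back to FVIII concentrate.

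- Synopsis, Criteria for Evaluation: "Values for hFVIII activity will be excluded if obtained within 72 hours since the last infusion of exogenous FVIII protein concentrates".
- Section 9.7.2.1: efforts to sample after a 72-hour interval are intended only for subjects at 5 IU/dL or more at 16 weeks "who have not resumed FVIII replacement therapy". Footnote c of Table 9.1.3 says the same.
- Section 9.1: for recurring bleeds, "the Investigator and Medical Monitor will discuss whether to resume prior FVIII prophylaxis".
- Section 14.2: if the endpoint is missing, the median in the subject's "last 4-week window containing a valid observation will be used". No exception is made for resumed prophylaxis.
- Section 14.2 names two sensitivity analyses for missing data, observed cases and MMRM, and leaves further detail to the SAP.

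Section 14.2 also reports the proportions at or above thresholds such as 5, 15, 25, 30 and 40 IU/dL.

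**The concern.** Each rule is reasonable alone. Together they make the endpoint missing because response was lost, and then fill it with a value that normally comes from before prophylaxis resumed. The subject's outcome at Weeks 49-52 is that endogenous FVIII no longer sufficed, but the analysis may record the level he had while it did.

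Section 14.2 uses a fixed 1 IU/dL baseline because activity cannot be measured reliably in subjects on prophylaxis. A subject back on concentrate at Week 52 presents the same measurement problem, but he gets an earlier post-infusion value instead. Section 14.3 takes the cautious line for FVIII use, where the missing change in "annualized utilization and annualized infusion rate will be imputed as 0". The primary endpoint has no such protection.

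At stake are the estimated mean activity and the threshold proportions, which carry the clinical reading of a single-arm trial. With about 16 subjects in the primary population, one or two such cases are visible.

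**Working it through.** **Plan's own figure.** Section 14.8: n = 16, effect size 0.8, one-sided 0.025, one-sample t-test. Noncentrality is 0.8 × √16 = 3.2 with 15 degrees of freedom. Power is 84.8%, so the stated 85% reproduces.

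**Step 1: how often is there no valid value?** The Synopsis and Section 7.3 give usual prophylaxis as 2 to 3 infusions a week. Section 12.6 schedules two visits in the window, Weeks 50 and 52. The spacing within the week and random visit timing are my assumptions.

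| Infusions per week | Gaps (h) | Share of week beyond 72 h | Chance of no valid value in two visits |
|---|---|---|---|
| 3 | 48, 48, 72 | 0/168 = 0% | 100% |
| 2 | 72, 96 | 24/168 = 14% | (1 - 24/168)² = about 73% |

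The last-window rule therefore applies to most subjects back on concentrate.

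**Step 2: effect on the mean.** Let k be the number of such subjects among 16 and v the carried-forward value. Compared with the 1 IU/dL baseline, the mean is higher by k(v-1)/16. The documents give neither k nor v, so a range is shown, in IU/dL:

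| k | v = 5 | v = 15 | v = 30 | v = 40 |
|---|---|---|---|---|
| 1 | 0.25 | 0.88 | 1.81 | 2.44 |
| 2 | 0.50 | 1.75 | 3.62 | 4.88 |
| 4 | 1.00 | 3.50 | 7.25 | 9.75 |

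**Step 3: effect on the proportions.** Each subject adds 1/16 = 6.25 points to every threshold that v meets. If k = 2, v is at least 5 and all other subjects exceed 5 IU/dL, the report reads 16/16 (exact 95% CI 79 to 100%) instead of 14/16 (62 to 98%).

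**Step 4: the named sensitivity analyses.** Take a mean change of 39 in the other subjects (Section 7.4 reports earlier means above 40 IU/dL; less 1 for baseline), with k = 2 and v = 15:

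- Subjects set to baseline: 39 × 14/16 = 34.1.
- Last-window rule: (39 × 14 + 14 × 2)/16 = 35.9.
- Observed cases: 39.0.

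Observed cases is the most optimistic of the three. MMRM uses these subjects' earlier values and relies on missing at random, which is doubtful when the value is missing because response was lost. Neither scores them low.

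**Step 5: effect on the test.** Assume lognormal levels with mean 40 and SD 39/0.8 = 48.75. With k = 4, simulated rejection is 95% with these subjects at 1 IU/dL and 97% with 15 IU/dL carried forward. The test against 0 hardly moves.

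**Step 6: who is not affected.** A subject who never reached 5 IU/dL carries forward a value below 5. He adds less than (5-1)/16 = 0.25 IU/dL to the mean and meets none of the listed thresholds.

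**The case against.** The strongest reply is that the size is assumed and may be small. Prophylaxis is reconsidered because of bleeding, and sampling is weekly to Week 26 and every 2 to 4 weeks afterwards. The last valid window may therefore lie close to resumption and already show low FVIII. If v is below 5, two such subjects move the mean by less than 0.5 IU/dL and change no threshold. That stands, and it is why the result is given as a range. It does not remove the problem, because nothing in the plan ensures that v is low. At two infusions a week there is also about a 27% chance of at least one valid value, in which case the rule is not used.

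The remedy can also be criticised: 1 IU/dL may understate real residual expression. That stands too, and supports showing both analyses.

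A reader might infer three stronger claims that the documents do not support.

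- That every failure is scored as a responder or removed in every planned analysis. The treatment-failure definition joins not achieving 5 IU/dL by Week 52 with "inability to maintain independence from prophylactic FVIII replacement therapy due to joint bleeding episodes", so on its natural reading such a subject carries a value below every threshold. The sensitivity list is also open, and the SAP is not shown.
- That carrying forward inflates results for other dropouts. Section 7.3.1 places the peak in the first 6 to 12 months, "followed by a decline to a steady-state level of expression thereafter". Weeks 49-52 fall at the end of that peak period, and an early dropout may carry forward a rising value. The direction is not determined.
- That a return to emicizumab has the same effect. The 72-hour exclusion covers FVIII concentrates only.

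Nor is the contrast with Section 14.3 uniform: missing bleeding-rate change there takes the median of observed changes, which is not a conservative rule.

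**Conclusion.** The point holds for one group: subjects who responded, lost response and resumed routine FVIII-concentrate prophylaxis. For them the stated rules usually replace the Weeks 49-52 value with an earlier one, and neither named sensitivity analysis corrects this. The overstatement is k(v-1)/16 in the mean and k/16 in each threshold proportion that v meets. For an assumed k = 2 and v between 5 and 40, that is 0.5 to 4.9 IU/dL and up to 12.5 points. The result depends on such subjects occurring and on their last valid window being above baseline, and the documents settle neither. The hypothesis test is not materially at risk. The plan should be fixed because the estimate and the proportions are what readers will use, but the flaw does not undermine the trial's primary test.

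**What to change.** In Section 14.2, and matched in the SAP, state that a subject on routine FVIII-concentrate prophylaxis during Weeks 49-52 with no valid value is assigned the 1 IU/dL baseline (change 0) and counted below every threshold. Keep the last-window rule for these subjects as a sensitivity analysis. Tie the rule to resumed prophylaxis without a valid value, not to the treatment-failure definition, which need not cover a subject who reached 5 IU/dL and then lost it.

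At minimum, pre-specify the baseline-imputed analysis of both the mean and the threshold proportions, reported beside the current rule.

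The cost is about one sentence in each document, with no change to visits, sampling or treatment. The reported mean and responder proportions may be slightly lower, and possibly conservative where some expression remains.

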14.3 Secondary Efficacy Endpoints

The analyses of the secondary efficacy endpoints will be descriptive. Mean and associated 95% confidence interval will be provided for the following secondary endpoints, where the baseline value will be derived from the data in the approximately 12-month period prior to BMN 270 infusion:

- For subjects receiving FVIII prophylaxis prior to study entry, change from baseline in the annualized utilization (IU/kg/year) of exogenous FVIII replacement therapy from Week 5 post BMN 270 infusion to last visit by data cutoff (for Week 52 analysis); and separately, for subjects receiving prior emicizumab prophylaxis, change from baseline in the annualized utilization (mg/kg/year) of emicizumab from Week 27 post BMN 270 infusion to last visit by data cutoff (for Week 52 analysis)
- For subjects receiving FVIII prophylaxis prior to study entry, change from baseline in the annualized infusion rate (number/year) of exogenous FVIII replacement therapy from Week 5 post BMN 270 infusion to last visit by data cutoff (for Week 52 analysis); and separately for subjects receiving prior emicizumab prophylaxis, change from baseline in the annualized utilization (mg/kg/year) of emicizumab from Week 27 post BMN 270 to last visit by data cutoff (for Week 52 analysis) infusion
- Change from baseline in the annualized number of bleeding episodes (number/year) requiring exogenous FVIII replacement treatment from Week 5 post-BMN 270 infusion to last visit by data cutoff (for Week 52 analysis) for subjects receiving prior FVIII prophylaxis, or from Week 27 post-BMN 270 infusion to last visit by data cutoff (for Week 52 analysis) for subjects receiving prior emicizumab prophylaxis from baseline

Mean change from baseline and associated 95% confidence interval will be calculated for the total score of Haemo-QoL-A at Week 52 post-BMN 270 infusion as well.

The missing value of the change for annualized utilization and annualized infusion rate will be imputed as 0. The missing value of the change for annualized number of bleeding episodes will be imputed using the median value of the changes of all observed cases.

A sensitivity analysis is planned to analyze ABR using a generalized linear mixed model assuming negative binomial as the underlying distribution. The model will include period (pre- to post-BMN 270 infusion) as the only factor, repeated within subject. The actual

number of bleeding episodes will be used as the dependent variable with the time period adjustment (annualization) being implemented as the offset.

To assess the impact of missing data, analyses using observed case are planned as sensitivity analyses for the secondary endpoints. Multiple imputation methods may also be performed.

